8.4 Tertiary objectives and outcome measures (subject to additional funding)

Objective	Outcome measure	Time point(s) of evaluation of this outcome measure (if applicable)
1.To compare the long-term serious adverse events related to treatments in both treatment arms	Long-term serious adverse events related to treatments	Up to 15 years post- randomisation
2.To determine disease progression beyond the prostate, including local spread and development of metastases	Time to disease progression (including local and distal recurrence)	Up to 15 years post- randomisation

3.To determine long-term	Time to disease-specific and	Up to 15 years post-
disease-specific and overall	overall mortality	randomisation
mortality		

8.5 Definition of primary treatment failure

Primary treatment failure will be determined by repeat prostate biopsies (either as part of the routine protocol-defined time point), or "for cause", or clinical appearance of symptoms demonstrating disease progression, or radiological concerns on repeat imaging, or due to clinical concern. Primary treatment failure is defined according to the treatment received:

Treatment Arm	Treatment received within arm	Definition of primary treatment failure	
Partial Ablation	HIFU or IRE	 Any of the following: a) persistent intermediate-risk PCa in a treated area after one repeat PA treatment b) repeat PA treatment requiring more than 75% of the prostate to be treated, and/or indication for radical treatment c) positive biopsies demonstrating high-risk PCa (Gleason Grade Group 4-5) at any time d) extra-prostatic disease progression defined by imaging, clinical examination, or biopsy findings e) the development of systemic disease requiring long-term androgen deprivation therapy 	
Radical Treatment	Radical prostatectomy (RP)	 Any of the following: a) a rising serum PSA reaching ≥0.2 ng/ml following initial reduction to <0.1 ng/ml after surgery b) a failure of serum PSA to fall below 0.1 ng/ml after surgery c) clinical progression to local recurrence/systemic disease d) the need for long-term androgen deprivation therapy 	
	Radical radiotherapy (RRT) or low dose- rate brachytherapy (LDR-B)	 Defined using the RTOG-ASTRO Phoenix criteria (48) as: a) a rise of post-treatment PSA ≥2.0 ng/ml above the post-treatment nadir or b) clinical progression to systemic disease with the need for long-term androgen deprivation therapy 	

Further information regarding diagnosis and management of primary treatment failure can be found in section 16.4.

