sign of the disease returning or worsening, additional treatments will be discussed and offered. We will compare how well the treatments work by measuring the time it takes for additional treatment to be necessary in the radical treatment arm, or to require treatment of the whole prostate gland, or other prostate cancer-specific treatment, in the PA arm. We will also assess quality of life using questionnaires, and costs to the NHS of each treatment.

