16.4 Additional treatment/treatment failure

Partial Ablation Arm

Where a positive biopsy result is returned for intermediate-risk PCa during the study follow-up period, either in the previously treated area or in a previously untreated area (demonstrating new intermediate-risk disease), participants will be offered ONE repeat PA treatment of the positive biopsy area.

Primary treatment failure following PA will be determined by repeat prostate biopsies – per protocol or "for cause" or clinical appearance of symptoms/signs/imaging demonstrating disease progression, or due to clinical concern. Biopsies will result in one of four pre-defined scenarios:

- Scenario 1: Negative biopsies, in which case the patient will continue to be followed-up as described.
- Scenario 2: Positive biopsies in a previously untreated or treated area of the prostate demonstrating low-risk low-volume disease, in which case the patient will not require additional treatment and follow-up will continue.
- **Scenario 3:** Positive biopsy for intermediate-risk PCa in the previously treated area, in which case the patient will be offered one repeat PA treatment of the positive biopsy area.
- **Scenario 4:** Positive biopsy for intermediate-risk PCa in a previously untreated area, demonstrating new intermediate-risk disease, in which case the patient will be offered one repeat PA treatment.

Refer to the flow chart below.

Radical treatment arm

For participants in the radical treatment arm receiving RP additional treatment, options will be discussed with the participant, as per standard NHS care. This is usually salvage radiotherapy post-RP with or without androgen deprivation therapy, or androgen deprivation alone. Salvage RP or androgen deprivation will usually be offered where appropriate if post-RRT or LDR-B treatment failure occurs, as per NHS standard care. Refer to flow charts below.

Management of primary treatment failure

Where treatment failure is diagnosed, the patient will be re-staged as appropriate with cross-sectional imaging, and additional appropriate treatment options will be discussed with the participant, as per standard NHS care. For participants in the PA arm these may include salvage RP, external beam RT, or long-term androgen-targeted therapy +/- chemotherapy. For patients in the radical therapy arm this may include an appropriate salvage therapy, or long-term androgen-targeted therapy +/- chemotherapy.

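### The RRT/LDR-B failure definition has no stand-alone criterion for clinical local recurrence and accepts systemic progression only with long-term ADT, so clinical relapse without a nadir + 2.0 PSA rise is missed or dated late.

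*Protocol*

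**What the plan says.** Sections 6 and 8.2 both send the reader to 8.5 for the definition of primary treatment failure, so 8.5 is where the co-primary endpoint is fixed. Its table has three rows.

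- **RRT or LDR-B**, two criteria, either of which suffices: (a) PSA at least 2.0 ng/ml higher than its lowest value since treatment; the other, (b), reads "clinical progression to systemic disease with the need for long-term androgen deprivation therapy".
- **RP**, four criteria: two based on PSA, then (c) "clinical progression to local recurrence/systemic disease" and (d) "the need for long-term androgen deprivation therapy".
- **PA**, five criteria, including (b) "repeat PA treatment requiring more than 75% of the prostate to be treated, and/or indication for radical treatment", (d) "extra-prostatic disease progression defined by imaging, clinical examination, or biopsy findings" and (e) systemic disease requiring long-term ADT.

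Section 19.2 takes its planning rates, for men having RP or RRT, from a notion of failure that covers clinical as well as biochemical relapse. Sections 13.2.3 and 13.2.4 call for re-staging when PSA has risen by 2.0 ng/ml or more above nadir. Section 9.2 also calls for re-staging at any point when progression is suspected, with no PSA threshold. Section 19.4 censors men without treatment failure.

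**The concern.** Two men in the same arm with the same clinical finding can be classified differently because one had surgery and the other radiotherapy. Local recurrence on its own is failure after RP but not after RRT or LDR-B. Systemic disease is failure at once after RP, but after RRT/LDR-B it also needs an indication for long-term ADT, unless the PSA criterion has been met.

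The choice between RP, RRT and LDR-B is made jointly by patient and clinicians (13.2.1) and is not a minimisation factor (15.3). The share of the radical arm under the narrower definition is therefore not controlled. Any event lost this way comes off the radical arm, which is the arm that the sample size assumes to have the lower failure rate (10% versus 20%).

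**Working it through.** The protocol states no figure on this point, so the main check is a comparison of the rows. Each event is taken alone, before any PSA criterion is met.

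| Event | PA | RP | RRT/LDR-B |
|---|---|---|---|
| Clinical local recurrence | Only through (a), (b) or (c) | Yes, (c) | No |
| Spread outside the prostate, not systemic | Yes, (d) | Yes, (c), as local recurrence | No |
| Systemic disease without long-term ADT | Through (d); (e) needs ADT | Yes, (c) | No |
| Need for long-term ADT without systemic disease | Not by itself | Yes, (d) | No |
| Indication for further radical treatment | Yes, (b) | No general criterion | No |

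The first four lines show that the RRT/LDR-B row is narrower than the RP row on every clinical event. The fifth is a contrast with PA only.

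**How an event is lost.** A man after RRT is re-staged under 9.2 because progression is suspected. Local recurrence is found with PSA at, say, 1.5 ng/ml above nadir, and he has further treatment. Neither (a) nor (b) is met. If his PSA then falls and stays down, 19.4 censors him as free of failure. If it later reaches nadir + 2.0, he becomes an event, but at a later date than the relapse.

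**What does not fill the gap.** The table cites the Phoenix criteria as reference 48, but the reference list ends at 39.

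**Illustration of size.** The protocol gives neither input, so both are assumptions: s, the share of the radical arm having RRT/LDR-B (30% to 70%), and m, the share of their failures that never meet (a) or (b) (5% to 30%). The same 10% true failure rate is assumed for every radical modality.

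- Planned hazard ratio: ln(0.90)/ln(0.80) = 0.4722, as in 19.2.
- Recorded radical-arm rate = 10% × (1 − s × m). Low end: 10% × (1 − 0.30 × 0.05) = 9.85%. High end: 10% × (1 − 0.70 × 0.30) = 7.9%.
- Of 400 × 10% = 40 radical-arm events, 40 × 0.015 = 0.6 to 40 × 0.21 = 8.4 are lost.
- Apparent hazard ratio: ln(0.9015)/ln(0.80) = 0.465 to ln(0.921)/ln(0.80) = 0.369.
- With equal true rates of 15% in both arms, the recorded radical rate is 14.775% to 11.85%, and the apparent hazard ratio is ln(0.85225)/ln(0.85) = 0.98 to ln(0.8815)/ln(0.85) = 0.78. With 360 men per arm after 10% dropout, events number 360 × (0.15 + recorded rate), about 107 to 97. Schoenfeld's formula, with 0.025 taken as two-sided, then gives a probability of p < 0.025 of about 0.026 to 0.16.

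The high end treats every affected event as lost rather than late, so it is an extreme and not an estimate.

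**The case against.** A reader might infer that events counted after PA or RP can never count after radiotherapy. The documents do not support that. Any such man whose PSA reaches nadir + 2.0 fails under (a), and that rise is the stated trigger for re-staging after RRT and LDR-B, so recurrences found by that route are already events. Scheduled mpMRI and biopsy belong to the PA arm only, which makes early detection of a radiotherapy recurrence less likely. Section 16.4 also places salvage after failure: "Salvage RP or androgen deprivation will usually be offered where appropriate if post-RRT or LDR-B treatment failure occurs". All this stands, and it limits the gap to relapse found before or without the PSA rise. It does not close the gap, because 9.2 permits re-staging on suspicion alone.

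A reader might also see a contradiction with the opening of 8.5, which names biopsy, symptoms, imaging and clinical concern, or with the lay summary, which speaks of "measuring the time it takes for additional treatment to be necessary in the radical treatment arm". Both are weak evidence. The opening of 8.5 lists routes of detection, 16.4 ties almost the same sentence to PA, and the table then defines failure by treatment received. The lay summary is a simplification that does not fit the RP row either, where PSA alone is failure.

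Nor is the comparison one-sided throughout. PA criterion (e) carries the same ADT condition, although (d) covers extra-prostatic progression without it. RP has no general salvage-treatment criterion. A PA man with intermediate-risk recurrence in the treated area is first offered repeat PA and has not yet failed. PA has no PSA failure criterion. So the direction of this one omission is certain, but it does not show that the endpoint as a whole favours radical treatment.

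Finally, time to disease progression, including local recurrence, is a secondary outcome in both arms (8.3, item 6), so these relapses would still be reported, though not in the co-primary endpoint.

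**Conclusion.** The point holds as a defect of wording in a co-primary endpoint. The RRT/LDR-B row is narrower than the RP row and narrower than the concept of relapse behind the planning rates in 19.2. The effect on the recorded radical-arm failure rate can only be downward. The number of men affected cannot be derived from the protocol and may be small. The illustrated range, from under 1 to about 8 of 40 radical-arm events, rests wholly on assumed shares and on counting late events as lost; it shows the direction and what the worst assumptions would do. The correction is cheap and worth making before analysis, but the evidence does not support calling the comparison seriously compromised.

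**What to change.** Amend the RRT/LDR-B row of 8.5 so that it agrees with the RP row and with 19.2. Keep the PSA criterion unchanged. List as separate endpoint criteria (i) clinical progression to local recurrence or systemic disease and (ii) need for long-term ADT for recurrence. The words *for recurrence* matter, because 13.2.3 allows ADT alongside primary radiotherapy and that must not be counted as failure.

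Do not add a general salvage-treatment criterion to the radical rows. RP has no local-recurrence gap to fill, and an event defined by a treatment decision would bring clinician discretion into the endpoint of an unblinded trial. No PSA threshold, re-staging trigger or other clinical management rule needs to change.

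The cost is a protocol amendment to the endpoint wording. Treatment failure, further treatment, progression and recurrence are already recorded on the CRF (16.4, 16.6, 18.5). The downside is a slightly higher recorded failure rate in the radical arm.

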8.6 The QuinteT Recruitment Intervention (QRI) – "The Information Study"

The PART study includes an integrated QuinteT Recruitment Intervention (QRI) which will be referred to as "The Information Study" to potential study participants. The aim of the QRI is to

understand/assess the recruitment process and how it operates in each recruiting site, so that sources of recruitment difficulties can be identified and suggestions made to change aspects of design, conduct or training that could then lead on to improvements in recruitment and informed consent.

Further information about the QRI can be found in section 10.

8.7 Use of core outcome sets

Maclennan (34) established a Core Outcome Set (COS) for trials of effectiveness in localised prostate cancer; outcomes reported in this COS are all being recorded for this study.

9 STUDY DESIGN AND SETTING

The PART study is a multi-centre, two arm, parallel design, randomised controlled clinical study. An embedded QuinteT Recruitment Intervention will be used to understand, monitor and address barriers to participation.

The study will recruit 800 men (400 in each of the 2 study arms) with PCa from approximately 10 sites in the UK. Participants will be randomised to receive partial ablation (HIFU or IRE) or radical treatment (radical prostatectomy (RP), radical radiotherapy RRT) or low dose-rate brachytherapy (LDR-B)).

A study flow chart is provided in

APPENDIX 1.

Within the radical treatment arm, the type of treatment the participant receives (i.e. radical prostatectomy, radical radiotherapy, or low dose-rate brachytherapy) will be determined through joint decision-making between the participant and clinical team, based on current guidelines. Within the PA arm, clinical factors such as the location of the tumour within the prostate gland will be assessed at the treatment planning stage in order to make a specific recommendation regarding which PA option (IRE and/or HIFU) is necessary on a case-by-case basis for PA treatment.

All participants randomised to PA will have their medical case reviewed by a "Partial Ablation Treating Planning Team" (see section 9.5) who will recommend the use of either IRE or HIFU (or in some cases either option), largely based on tumour location in the prostate gland, along with treatment planning aspects. As part of this process, patients may be referred for their PA treatment (IRE or HIFU) at another PART centre delivering that PA modality. In order to facilitate this expert review of PA cases ahead of treatment for participants randomised to PA, and/or as part of the treatment process, patient information (including clinico-pathological data and radiological images) may be transferred securely between NHS centres involved in PART, as is the case in standard-of-care when patients' care is transferred from one NHS Trust to another.

Follow-up will be conducted using standard NHS care protocols for the radical treatment group, and a combination of mpMRI and repeat targeted and/or systematic prostate biopsies in the PA group. Following treatment for PCa, participants will be actively followed-up/monitored for treatment failure in accordance with usual NHS care. All participants will undergo regular blood tests for PSA levels, and for participants randomised to the PA arm, follow-up will also consist of mpMRI and prostate biopsies in accordance with the schedule of study assessments; in-person clinic visits are required for these.

The number of visits per participant will vary and will be dependent on which treatment they are allocated to.

Participants will be followed-up in the study for as long as the study remains open – for those recruited early in the study this may be for 5 years post-randomisation. All participants will have a minimum of 12 months follow-up. Additional funding for longer-term follow-up will be sought in a new funding application in due course. All patients will continue with standard-of-care NHS follow-up beyond the time duration of the study. Any patients with less than 3 years 'on study' follow up will continue to receive necessary PSA tests, MRI and other imaging, and prostate biopsy as necessary, and/or any additional investigations or treatment, in NHS standard of care pathways beyond the timescale of this study.

9.1 Recruiting sites/site types

Approximately 10 urology centres (within NHS secondary care hospitals in the United Kingdom) who see patients with PCa will recruit participants into the PART study.

In order to take part in the study, recruiting centres need to be able to offer radical treatment +/- PA* to PCa patients.

*PA therapy does not need to take place in each recruiting centre; if the method of PA treatment recommended by the PA Treatment Planning Team is not available locally within the recruiting centre, the participant will be referred to an appropriate nearby centre delivering this therapy within a model of PART centre co-operation.

PART_Protocol_V3.0_15May2024_Clean.docx Page **25** of **77**

Participants may receive some of their treatment at other NHS sites; such treatment will be arranged in accordance with usual care practice by the recruiting site e.g. participants randomised to radiotherapy treatment will have their radiotherapy scheduled in accordance to the usual care arrangements for that recruiting site. The recruiting site will be responsible for completion of the case report form; any sites undertaking treatment that is standard of care or within usual care competence will be required to transfer data to the recruiting site as required for completion of the CRF. An appropriate agreement will be put in place for these sites.

9.1.1 Participant Identification Centres

Participant Identification Centres (PICs) will not be used in this study. The identification of participants will be done by the recruiting centres, including at regional prostate cancer multi-disciplinary team (MDT) meetings, as described below in Section 12.1.

9.2 Collection of outcome data and follow-up assessments

Participants will undergo research specific visits and receive communications from the PART study team to collect outcome data.

Participants will subsequently be followed up in clinic approximately **six weeks post-operatively** and **three-monthly** post-treatment in the first year, and then approximately every **6 months** as per routine NHS care for up to 5 years post-randomisation depending upon when they are recruited into the study. If, at any point, disease progression is suspected, the patient will be re-staged as per NHS standard care.

Participants receiving PA will be required to attend in-person follow-up clinic visits for mpMRI at 1 week, 6 months, 12 months and 36 months[#] post- treatment and for prostate biopsies at 12 months and 36 months[#] (targeted and/or systematic, depending on mpMRI result).

Participants will be sent HRQoL questionnaires (PORPUS, IPSS, EPIC, EQ-5D-5L, and MAX-PC (modified 18 item)), and health care use questionnaires to complete electronically (a postal option will also be made available where required) at 6 weeks post-treatment and at 3 months, 6 months, 12 months, 24 months[#] and 36 months[#] post- randomisation.

Treatment complications and unexpected serious adverse events related to the study intervention will be collected using a combination of medical notes review, Health Care Use Questionnaire review and asking patients at follow-up appointments, and/or when a member of the research team becomes aware that a serious adverse event has occurred.

For participants who have undergone treatment using PA, additional imaging and repeat biopsies could also be triggered by a rise in PSA of at least 50% over a period of 12 months, or due to clinical concern.

Refer to section 16 for full details of outcome data collection and follow-up assessments.

[#]24-month and 36-month follow-up of all 800 participants is subject to receipt of additional funding for longer-term follow-up, and may not be collected for all participants. These participants will continue with standard-of-care NHS follow-up beyond the time duration of the study. Any patients with less than 3 years 'on study' follow up will continue to receive necessary PSA tests, MRI and other imaging, and prostate biopsy as necessary, and/or any additional investigations or treatment, in NHS standard of care pathways beyond the timescale of this study.

PART_Protocol_V3.0_15May2024_Clean.docx Page **26** of **77**

9.3 Duration of participant involvement

Participants will be in the currently-funded study for approximately 3 years median from commencement of the randomised treatment allocation, and for a minimum of 12 months follow-up 'in study' for the last recruited patient.

9.4 Post-study treatment/care and follow-up

At the end of the study participants will receive standard care as per that provided by their NHS site.

9.5 Partial Ablation Treatment Planning Team

All participants randomised to PA will be reviewed by a **PA treatment planning team** consisting of a clinician with expertise in PA delivery, and a radiologist. The PA treatment planning team will review the diagnostic biopsy report and MRI imaging of trial participants, and will recommend the use of IRE or HIFU (or either), largely depending on the tumour location in the prostate gland, along with other relevant clinical factors, along with treatment planning aspects.

9.6 Use of NHS Digital data (including data from registries)

Subject to additional funding, Hospital Episode Statistics (HES) and national mortality records data will be used to monitor long-term outcomes (anticipated up to 15 years). Participants will be asked to consent to the collection of their NHS/CHI number and use of other details for this purpose.

9.7 Health economics analysis

A health economic evaluation will assess the health care resource utilisation, cost impact and costeffectiveness in terms of cost per QALY of treating PCa patients using PA compared with radical treatment.

Using an NHS perspective for the baseline analysis, data will be collected on health care resource use via a questionnaire to be completed by participants. Costs will be estimated using a standardised approach. Data will also be collected on HRQoL using the EQ-5D-5L questionnaire. A "within-trial" cost-utility analysis will be conducted comparing the implementation of PA therapy with standard radical treatment for PCa participants.

